**Table 10: Exclusionary Laboratory Values**

Laboratory Parameter		Exclusion Criterion
Hematology		
a	Platelets	$\leq 75 \times 10^9/L$ (transfusion allowed with a 2-week washout period)
b	Hemoglobin	$\leq 9.0 \text{ g/dL}$ (transfusion allowed with a 2-week washout period)
c	ANC	$\leq 1.5 \times 10^9/L$
Hepatic		
e	ALT	$\geq 3 \times \text{ULN}$ ( $> 5 \times \text{ULN}$ for liver metastasis)
f	AST	$\geq 3 \times \text{ULN}$ ( $> 5 \times \text{ULN}$ for liver metastasis)
g	Total bilirubin	$\geq 1.5 \times \text{ULN}$ ( $\geq 2.5 \times \text{ULN}$ if Gilbert's syndrome or liver metastasis)
h	Alkaline phosphatase	$\geq 3 \times \text{ULN}$
Renal		
i	Serum creatinine clearance	$\leq 30 \text{ mL/minute}$ based on Cockcroft-Gault formula.
Chemistry		
j	Serum phosphate	$> \text{ULN}$
k	Serum calcium	Outside of normal range or serum albumin-corrected calcium outside of the normal range when serum albumin is outside of the normal range.

10. History of calcium and phosphate hemostasis disorder or systemic mineral imbalance with ectopic calcification of soft tissues (exception: commonly observed calcifications in soft tissues such as the skin, kidney tendon, or vessels due to injury, disease, or aging in the absence of systemic mineral imbalance).
11. Significant gastrointestinal disorder(s) that could interfere with absorption, metabolism, or excretion of pemigatinib.
12. Inability to swallow and retain oral medication.
13. Clinically significant or uncontrolled cardiac disease, including unstable angina, acute myocardial infarction within 6 months from Day 1 of study drug/treatment administration, New York Heart Association Class III or IV congestive heart failure, and uncontrolled arrhythmia (participants with pacemaker or with atrial fibrillation and well-controlled heart rate are allowed).
14. History or presence of an abnormal ECG that, in the investigator's opinion, is clinically meaningful. A screening QTcF interval  $> 480 \text{ ms}$  is excluded. For participants with an intraventricular conduction delay (QRS interval  $> 120 \text{ ms}$ ), the JTc interval may be used in place of the QTc with medical monitor approval. The JTc must be  $\leq 340 \text{ ms}$  if JTc is used in place of the QTc.

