**Table 12: Guidelines for Interruption and Restarting of Study Drug**

Adverse Event	Action Taken
Chemistry	

 
AST and/or ALT is <math>> 5.0 \times</math> ULN.
 
 
Note: In participants with liver metastasis-related elevations at baseline, contact sponsor to discuss clinical management and possible dose reductions.
	
Step 1: Interrupt pemigatinib up to 2 weeks (14 days) until the toxicity has resolved to <math>\leq</math> Grade 1 except by approval of the medical monitor.
 
Step 2: Restart pemigatinib at same dose. If assessed as related to pemigatinib, restart pemigatinib at next lower dose; monitor as clinically indicated.

Other toxicities	

 
Any Grade 1 or Grade 2 toxicity.
 
	
Continue pemigatinib treatment and treat the toxicity; monitor as clinically indicated.

 
Any Grade 3 toxicity, if clinically significant and not manageable by supportive care.
 
	
Step 1: Interrupt pemigatinib up to 2 weeks (14 days), until toxicity resolves to <math>\leq</math> Grade 1.
 
Step 2: Restart pemigatinib at same dose. If assessed as related to pemigatinib, restart pemigatinib at next lower dose; monitor as clinically indicated.

 
Any recurrent Grade 3 toxicity after 2 dose reductions.
 
	
Discontinue pemigatinib administration and follow-up per Protocol. (Exceptions require approval of sponsor.)

 
Any other Grade 4 toxicity.
 
QT/QTc to <math>> 500</math> milliseconds or to <math>> 60</math> milliseconds over baseline.
 
	
Discontinue pemigatinib administration and follow-up per Protocol.

The sponsor recommends a maximum of 2 dose level reductions: participants administered 13.5 mg can decrease to 9 mg, and if additional dose reduction is required, participants can decrease to 4.5 mg. Dose reductions below 4.5 mg are not allowed. The frequency of dosing remains the same (QD) as well as the schedule (continuous dosing). After a dose reduction, a dose re-escalation is not permitted.

For participants who are up-titrated from 13.5 mg to 18 mg, study drug can be decreased to 13.5 mg, and if additional dose reductions are required, participants can decrease to 9 mg and then to 4.5 mg. Dose reductions below 4.5 mg are not allowed.

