### 6.5.4. Criteria for Permanent Discontinuation of Study Drug

The occurrence of unacceptable toxicity not caused by the underlying disease will require that the study drug be permanently discontinued. Unacceptable toxicity is defined as follows:

- Occurrence of an AE that is related to study drug that, in the judgment of the investigator or the sponsor's medical monitor, compromises the participant's ability to continue study-specific procedures or is considered to not be in the participant's best interest.
- An AE requiring more than 2 dose reductions.
- Persistent AE requiring a delay of therapy for more than 2 weeks (14 days) unless a greater delay has been approved by the sponsor.
- Increase in QT/QTc to  $> 500$  milliseconds or to  $> 60$  milliseconds over baseline. In case of a QTc  $> 500$  milliseconds, the participant must be hospitalized and continuous ECG monitoring must be set up until the measure of the QTc interval decreases below 500 milliseconds and is acceptable in the opinion of the local cardiologist.

See Section 7 for discontinuation procedures.

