### **8.3.4. Electrocardiograms**

Single 12-lead ECG will be obtained as outlined in the SoA (see Table 3) using an ECG machine that automatically calculates the heart rate and measures PR, QRS, QT, and QTc intervals. All 12-lead ECGs will be performed with the participant in a recumbent or semirecumbent position after approximately 5 minutes of rest.

The 12-lead ECGs will be interpreted by the investigator at the site to be used for immediate participant management. Additional 12-lead ECGs may be performed as clinically indicated to manage participant safety. The decision to include or exclude a participant or withdraw a participant from the study treatment based on an ECG flagged as "Abnormal, Clinically

"Significant" is the responsibility of the investigator, in consultation with the sponsor's medical monitor, as appropriate. Clinically notable abnormalities that are considered clinically significant in the judgment of the investigator are to be reported as AEs. In the event that a single QTc is > 480 ms at screening, the participant may enroll if the average QTc for the 3 ECGs is  $\leq$  480 ms or with approval from the medical monitor. For participants with an intraventricular conduction delay (QRS interval > 120 ms) at screening, the JTc interval may be used in place of the QTc with medical monitor approval. The JTc must be  $\leq$  340 ms if JTc is used in place of the QTc. In addition, the JTc interval should be used for all subsequent assessments.

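### For participants entered and followed on JTc, the 500 ms stopping limit and, above all, the hospitalization and release rule exist only on the QT/QTc scale

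*Protocol*

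**What the plan says.** Entry. Exclusion criterion 14 (Protocol 5.2) excludes a screening QTcF above 480 ms. For a QRS above 120 ms it adds that "the JTc interval may be used in place of the QTc with medical monitor approval", with JTc then limited to 340 ms. Section 8.3.4 repeats this route ("340 ms if JTc is used in place of the QTc") and extends it to follow-up: "the JTc interval should be used for all subsequent assessments".

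Stopping. Protocol 6.5.4 defines unacceptable toxicity to include an "Increase in QT/QTc to" more than 500 ms, or more than 60 ms over baseline. Table 12 carries the same two limits, and the action is "Discontinue pemigatinib administration and follow-up per Protocol". Section 7.1.1 lists unacceptable toxicity among the reasons for which treatment must stop.

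Hospitalization. For a QTc above 500 ms, 6.5.4 requires that "the participant must be hospitalized and continuous ECG monitoring must be set up until the measure of the QTc interval decreases below 500 milliseconds". The value must also be acceptable to the local cardiologist. This rule has no change-from-baseline alternative.

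Analysis. SAP 8.5 counts QT and QTc outliers at more than 450 ms, more than 500 ms, or a rise of more than 30 ms, and its Table 6 sets the high QTc threshold at 460 ms. JTc appears in neither place. Protocol 8.3.4 lists PR, QRS, QT and QTc as the intervals the ECG machine measures.

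**The concern.** The protocol deliberately admits participants whose QTc is inflated by a wide QRS and moves them to another interval for the whole study. The on-treatment limits do not move with them. No section gives a JTc value for stopping, hospitalization or release, or says how a QTc limit applies to someone followed on JTc.

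A site therefore has two readings, and neither works as a safety rule. Staying on QTc departs from 8.3.4 and can place a participant above the limit before the first dose. Switching to JTc compares 500 ms with an interval whose entry ceiling is 340 ms. At stake is consistent application of a mandatory rule across sites, in participants with existing conduction delay. In the SAP, a pre-existing delay could be reported as QTc prolongation.

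**Working it through.** The plan states no figure to reproduce; the check is interval arithmetic.

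**Inputs**
- QRS above 120 ms and JTc at most 340 ms for the JTc route (exclusion 14; 8.3.4).
- Ordinary screening ceiling, QTcF 480 ms (exclusion 14).
- On-treatment limits: above 500 ms, or more than 60 ms over baseline (Table 12; 6.5.4).
- Hospitalization above 500 ms; release requires QTc below 500 ms (6.5.4).
- SAP cuts: 450 ms and 460 ms (SAP 8.5; SAP Table 6).
- Assumption: JTc = QTc − QRS, because the documents do not define JTc. The QRS values are illustrative.

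**Reading A: the 500 ms limit applied to QTc.** QTc = JTc + QRS, so a participant is above 500 ms at entry when QRS > 500 − JTc.

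| JTc at entry (ms) | QRS above which QTc exceeds 500 ms |
|---|---|
| 340 | 160 |
| 320 | 180 |
| 300 | 200 |

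At JTc 340, QTc is 340 + 121 = 461 ms at QRS 121, 480 ms at QRS 140, 500 ms at QRS 160 and 510 ms at QRS 170. With QRS from 121 to 160 ms, QTc cannot exceed 340 + 160 = 500 ms at any permitted JTc, so the breach at entry is confined to wider QRS. Where it occurs, release fails too: with QRS fixed at 170 and JTc unchanged at 340, QTc stays at 510 ms and does not fall below 500 ms.

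**Reading B: the 500 ms limit applied to JTc.**
- Rise needed from the entry ceiling: more than 500 − 340 = 160 ms. From JTc 300: more than 200 ms.
- The same step on the QTc route, from its ceiling: more than 500 − 480 = 20 ms.
- At QRS 140, JTc 500 corresponds to QTc 500 + 140 = 640 ms.

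**The change limit.** Change in QTc = change in JTc + change in QRS. If QRS is stable, the two changes are equal and the 60 ms limit carries over without a new figure: it is passed above JTc 400 from 340, or above 360 from 300. That is well before 500 ms, so under Reading B the absolute limit adds nothing for stopping. If QRS widens on treatment, the two changes differ by the amount of widening, and the choice of interval matters here as well.

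**Hospitalization.** Its only trigger is the absolute value, so nothing carries over. The gap is greatest here.

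**SAP.** At JTc 340, QTc exceeds 460 ms when QRS > 460 − 340 = 120 ms, which is every participant on this route at the entry limit. With QRS 121, QTc is 461 ms, above both the 450 ms outlier cut and the 460 ms threshold with no change on treatment.

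**The case against.** The strongest reply is that the protocol already protects these participants. JTc entry needs case-by-case approval. Exclusions 13 and 14 remove uncontrolled arrhythmia and clinically meaningful ECG abnormalities. Section 8.3.4 gives ECG-based withdrawal to the investigator, in consultation with the medical monitor as appropriate. Section 6.5 calls for clinical judgment and may exempt events with a clear alternative explanation from dose-reduction rules. The 60 ms limit still works. All of this stands, but none of it supplies an absolute on-treatment limit or a release condition on JTc. The exemption in 6.5 concerns dose reduction, whereas stopping under 6.5.4 and 7.1.1 is mandatory. The QT/QTc entry in Table 12 has no exception wording, unlike its entry for recurrent Grade 3 toxicity.

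Three stronger readings are tempting, and the documents do not support them.

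- *Stopping is disabled for JTc participants.* It is not, because the 60 ms limit can be carried over while QRS is stable.
- *Eligible participants generally meet the stopping rule at baseline.* This needs QRS above 160 ms even at the JTc ceiling, and a wider QRS below it. Section 6.5.4 also speaks of an "Increase in QT/QTc to" the limit, so an unchanged pre-treatment value may not literally trigger stopping. Table 12 omits the word for increase, and the hospitalization sentence depends only on the QTc value, so the text is not uniform.
- *A participant stopped this way counts as a non-responder in ORR.* Stopping drug does not do that. Imaging continues after discontinuation for reasons other than progression (Protocol 8.2.1, 8.8.2), and SAP 7.2.1.2 counts assessments up to new anticancer therapy.

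**Conclusion.** The concern holds as an inconsistency between the entry and follow-up interval and the on-treatment limits. It affects the absolute 500 ms stopping limit and, most sharply, hospitalization and release. On QTc, the limit is exceeded before dosing when QRS > 500 − JTc, and release is then out of reach with unchanged intervals. On JTc, the trigger needs a rise of more than 160 ms from the entry ceiling. The SAP has a related gap, since it can count a pre-existing conduction delay as a QTc outlier.

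This rests on JTc = QTc − QRS and, for the 60 ms limit, on a stable QRS. The documents give neither the frequency of QRS above 120 ms nor the number expected to enter on JTc; it may be small. The primary analysis is not affected. Correction is still worthwhile, because a mandatory safety rule misfires under either reading for participants the protocol chooses to admit.

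**What to change.** Exclusion 14, Section 8.3.4, Table 12 and Section 6.5.4 must be reconciled. For participants entered on JTc, the sponsor should define how JTc is calculated and state which interval governs each of four items: the absolute stopping limit, the change-from-baseline limit, the hospitalization trigger and the release condition. Where JTc is meant, its value should be given. The choice of interval and value is a clinical one for the sponsor, and none is proposed here.

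SAP 8.5 should identify participants entered on JTc and summarise them on that interval, so that a conduction delay present at entry is not read as a QTc outlier.

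The cost is a few words in Table 12 and 6.5.4, one line in the SAP and a record of the entry basis. The eCRF is not among the documents, so that record may already exist. No new measurement is needed, since JTc can be derived from QT and QRS values already collected.

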### **8.3.5. Comprehensive Eye Examination**

A comprehensive eye examination should be performed by a qualified ophthalmologist at screening, once every 3 cycles ( $\pm$  7 days, starting at Cycle 3), at EOT, and as clinically indicated. The eye examination should include a visual acuity test, slit-lamp examination, and funduscopy with digital imaging and OCT. Visual acuity, slit-lamp, funduscopy and OCT are required to be performed at baseline and once every 3 cycles (starting with cycle 3) and more often if participants report any visual AEs or change in visual acuity. Every effort should be made to ensure that all subsequent examinations are performed by the same ophthalmologist.

### **8.3.6. Laboratory Assessments**

See [Table 15](#) for the list of clinical laboratory tests to be performed, and see the SoA ([Table 4](#)) for the timing and frequency. A central laboratory will analyze all [REDACTED] translational samples. The site's own local laboratories will perform all clinical laboratory assessments for safety (ie, blood chemistries, hematology assessments, coagulation tests, endocrine function and urinalysis).

Serum phosphate testing is required on Day 8 in Cycles 2+ if a participant develops hyperphosphatemia during Cycle 1 or in later cycles if the participant is up-titrated. Parathyroid hormone (endocrine) testing is required at baseline and Day 1 of every third cycle (starting with Cycle 3) as parathyroid hormone plays a role in calcium and phosphate hemostasis ([Khundmiri et al 2016](#)).

Additional testing may be required by the sponsor based on emerging safety data. All Protocol-required laboratory assessments must be conducted in accordance with the Laboratory Manual and the SoA (see [Table 4](#)). Information regarding collection, processing, and shipping of laboratory assessments is provided in the Laboratory Manual.

Clinically significant abnormal laboratory findings are those that are not associated with the underlying disease, unless judged by the investigator to be more severe than expected for the participant's condition. All laboratory tests with values considered clinically significantly abnormal during participation in the study or within 30 to 35 days after the last dose of study treatment should be repeated until the values return to normal or baseline or are no longer considered clinically significant by the investigator or medical monitor.

Screening laboratory assessments for hematology, chemistry, and coagulation must be performed within 14 days of Cycle 1 Day 1. If performed more than 14 days before Cycle 1 Day 1, then the tests must be repeated; if performed within 3 days of C1D1, additional laboratory sample testing is not required (see [Table 4](#)). Laboratory samples collected on study Day 1 must be performed

before study treatment administration. After Cycle 1, predose laboratory procedures can be conducted up to 72 hours before study treatment administration (within the 3-day study window), and results should be reviewed by the investigator or qualified designee and found to be acceptable before a new cycle of treatment is initiated.

See Section 9.1 for information regarding laboratory abnormalities that should be recorded as an AE in the eCRF. Additionally, if laboratory values from laboratory assessments performed at the institution's local laboratory require a change in participant management (eg, require treatment), or are considered clinically significant by the investigator (eg, SAE or AE or dose modification, see Section 9.2), then the result(s) of the **specific laboratory assessment(s)** must be recorded in the eCRF.

**Table 15: Required Laboratory Analytes**

Serum Chemistries	Hematology	Urinalysis With Microscopic Examination	Serology	Coagulation
Albumin	Complete blood count, including:	Color and appearance	Hepatitis B surface antigen	PT
Alkaline phosphatase		pH and specific gravity	Hepatitis B surface antibody	PTT or aPTT
ALT	• Hemoglobin	Bilirubin	Hepatitis B core antibody	INR
AST	• Hematocrit	Glucose	HCV antibody	
Amylase	• Platelet count	Ketones	NOTE: If any of the above are positive, HBV-DNA, HCV-RNA may be done to assess risk of reactivation, if indicated (eg, no history of immunization)	
Bicarbonate or CO 2 (not applicable for Japan)	• Red blood cell count	Leukocytes		
Blood urea nitrogen or urea	• White blood cell count	Nitrite		
Calcium	Differential count, including:	Occult blood		
Chloride	• Basophils	Protein		
Creatinine	• Eosinophils			
Glucose	• Lymphocytes			
Lactate dehydrogenase	• Monocytes			
Lipase	• Neutrophils			
Magnesium	Absolute values must be provided for:			
Phosphate	• WBC differential laboratory results			
Potassium				
Sodium				
Total bilirubin				
Direct bilirubin (if total bilirubin is elevated above ULN)				
Total protein				
Uric acid				
Vitamin D (25-hydroxyvitamin D and 1,25-dihydroxyvitamin D)				

Note: Additional tests may be required, as agreed upon by the investigator and sponsor, based on emerging safety data.

### **8.3.6.1. Pregnancy Testing**

[figure not shown]
A serum pregnancy test will be required for all women of childbearing potential during screening and at the EOT visit; participants going into hospice are not required to provide EOT pregnancy test. Urine pregnancy tests will be performed locally on Day 1 of each cycle, as outlined in [Table 4](#), as medically indicated (eg, in case of loss of menstrual cycle, when pregnancy is suspected), or per country-specific requirement (note that country-required urine pregnancy testing will be outlined and communicated to investigational sites under separate cover). If a urine pregnancy test is positive, the results should be confirmed with a serum pregnancy test.

If the serum pregnancy test is negative after a urine test was positive, the investigator will assess the potential benefit/risk to the participant and determine whether it is in the participant's best interest to resume study drug and continue participation in the study.

If a pregnancy is confirmed by a serum pregnancy test, see Section [9.5](#) for reporting requirements.

### **8.3.6.2. Serology**

Hepatitis screening assessments will be performed at the screening visit to assess infection and viral status; required analytes are shown in [Table 15](#). Generally, hepatitis tests should be performed early in the screening process due to the length of time needed to obtain the results. Additional tests may be performed if clinically indicated.

## 8.5.

## Translational Assessments

[figure not shown]
### 8.5.1. Tumor for Genomics Testing for FGFR Genetic Alterations and Gene Expression

[figure not shown]
All potential participants must be evaluated for activating FGFR mutations and rearrangements before enrollment. Participants with local genomics laboratory test results (within 24 months from date of screening) documenting an activating FGFR1-3 mutation or rearrangement are eligible (see [Appendix C](#)). Confirmatory testing through the central genomics laboratory will be performed on all participants; results from the central laboratory are not required before enrollment. Participants who have a commercial report from the central laboratory (Foundation Medicine, Inc) at screening (within 24 months of screening) will not need to send a sample for confirmatory testing (a biopsy will still be required for other testing). Details for sample collection, processing, and shipping will be provided in the Laboratory Manual.

[Appendix C](#) contains a list of the most common recurrent activating FGFR mutations (excluding the kinase domain) that have been previously described, are present in somatic mutation databases, and/or are homologous to activating mutations present in another FGFR. [Appendix C](#) is not all-inclusive, as extremely rare or novel activating alterations may not be present in the list. For FGFR mutations not present in [Appendix C](#), participants will be assigned to Cohort C unless the investigator consults with the study sponsor.

 Buccal swab DNA

may be used to confirm somatic mutations identified in tumor tissue.

#### 8.5.5. Tissue Biopsies

Mandatory tumor biopsies will be collected as specified below:

- **Screening:** Tumor tissue will be collected during screening. A fresh biopsy at screening is preferred; however, formalin-fixed paraffin embedded tissue is acceptable as long as the sample has been collected less than 24 months from date of screening.

*Note:* Fresh tumor biopsies should be taken from nontarget lesions when possible.

- **On-treatment:** An on-treatment biopsy should be collected during Cycle 2, between Day 7 and Day 14, but is allowed to be taken at any cycle; the on-treatment biopsy must be performed on a study drug administration day, preferably between Day 7 and Day 14.

*Note:* On-treatment biopsies should be taken from the same site as the screening biopsy whenever possible.

- **End of Treatment:** A biopsy at EOT/the time of progression is requested but not required from all participants. If EOT occurs less than 6 weeks after the on-treatment biopsy was performed, an EOT biopsy should not be performed.

If a participant is selected for inclusion in the biopsy cohort and it is subsequently determined that tissue cannot safely be obtained, the participant may still enroll for evaluation of safety and efficacy. Additional participants may be enrolled for paired biopsies if sufficient tissue for analysis are not obtained from any participant previously enrolled for biopsy.

